### **8.2.3 Expansion phase**

Sample size for the expansion cohort will be a minimum of 9 patients and a maximum of 22 patients (Simon's two-stage design, see statistical plan).

The 6 patients treated at the final dose from the run-in cohort will be included in statistical comparisons. This would yield a minimum total sample size of 15 patients, and a maximum sample size of 28 patients treated at the MTD schedule across the run-in and expansion phases, assuming 6 patients treated at the MTD schedule in the run-in and 22 patients treated at MTD schedule in the expansion cohort.)

The rate of completion of all adjuvant therapy by patients treated at the MTD schedule will be determined and compared to a historical control rate of 52%.

### **8.2.4 Statistical plan**

Simon's two-stage design will be used to test the primary endpoint for the phase II study. The null hypothesis that the completion rate is 0.5 will be tested against a one-sided alternative 0.7. In the first stage, 15 patients will be accrued (including 6 patients at MTD schedule from the run-in phase). If there are 7 or fewer completions in these 15 patients, the study will be stopped. Otherwise, 13 additional patients will be accrued for a total of 28 patients accrued in the expansion phase. The null hypothesis will be rejected if 18 or more completions are observed in 28 patients. This design yields a type I error rate of 0.09 and power of 80% when the true completion rate is 0.7.

We propose that the final decision about the direction of future strategy and additional expansion studies should be made based on careful analysis of subpopulations with particular attention to feasibility, toxicity, and observed immunodulatory responses.

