## 8.2 Determination of Sample Size and Accrual Rate

### 8.2.1 Sample Size and Power Estimate

We expect the true completion rate of this combined chemoradiation-nivolumab regimen followed by adjuvant nivolumab to be 70%, versus the null hypothesis of 50% (the rate of completion of a standard adjuvant cisplatin-based platform is 52%).

Simon's two-stage design will be used to test this endpoint. In the first stage, 22 patients will be accrued. If 11 or fewer completions, the study will be stopped. Otherwise, 18 additional patients will be accrued for a total of 40 participants.. The null hypothesis will be rejected if 26 or more completions are observed in 40 patients. This design yields a type I error rate of 0.05 and power of 80% when the true completion rate is 0.7.

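### Section 8.2 gives two complete but incompatible Simon two-stage designs for the primary endpoint (22 then 40 patients, and 15 then 28) and does not say which one governs

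*Combined protocol and SAP*

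**What the plan says.** Section 8.2.1 sets a null of 50% against an expected 70%. Stage 1 has 22 patients: "If 11 or fewer completions, the study will be stopped". Otherwise 18 more are accrued, making 40, and "The null hypothesis will be rejected if 26 or more completions are observed in 40 patients". The stated type I error is 0.05 and the stated power 80%.

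Section 8.2.4 sets the same null and alternative, one-sided. Stage 1 has 15 patients, of whom 6 come from the run-in at the MTD schedule: "If there are 7 or fewer completions in these 15 patients, the study will be stopped". It goes on: "Otherwise, 13 additional patients will be accrued for a total of 28 patients accrued in the expansion phase", and "The null hypothesis will be rejected if 18 or more completions are observed in 28 patients". Its operating characteristics are given as: "This design yields a type I error rate of 0.09 and power of 80% when the true completion rate is 0.7".

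Section 8.2.3 follows the smaller design: "Sample size for the expansion cohort will be a minimum of 9 patients and a maximum of 22 patients". With the 6 run-in patients this gives 15 to 28, and the section refers the reader to the statistical plan, which is the title of 8.2.4.

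The abstract and 3.4 give a maximum of 40 evaluable patients with type I error 0.05 and power 80%. Sections 8.2.5 and 8.2.6 repeat the 40. None of these four places gives stage-1 or rejection boundaries.

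Section 8.2.5 counts a patient as evaluable after any amount of study drug and allows replacement only of patients who leave before receiving nivolumab. Section 8.4.1 limits the primary endpoint to patients with at least one cycle (14 days) at the MTD schedule. Section 8.4.2 defines completion but gives no decision rule.

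**The concern.** The stage-1 look, futility bound, final size, success threshold and type I error of the primary test each have two values. No sentence ranks the two rules, withdraws one, or makes one a stage of the other. Arithmetic does not expose either as a slip, because each set of boundaries delivers its stated power and keeps within its stated error rate.

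The study is single-arm and open-label, so completions are visible as they accrue. With two written rules, a team could stop, continue or claim success and cite the protocol in each case. The false-positive rate would then no longer be fixed in advance.

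**Working it through.** **Inputs.** From 8.2.1: n1 = 22, stop if X1 ≤ 11, n = 40, reject if X ≥ 26. From 8.2.4: n1 = 15, stop if X1 ≤ 7, n = 28, reject if X ≥ 18. Both use p0 = 0.50 and p1 = 0.70.

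**Formula.** With r1 the stage-1 stopping bound and r the rejection bound, P(reject | p) = Σ over x1 > r1 of Bin(x1; n1, p) × P(X2 ≥ r − x1), where X2 ~ Bin(n − n1, p).

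**The plan's own figures.**

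| | 8.2.1 (22/11, 40/26) | 8.2.4 (15/7, 28/18) |
|---|---|---|
| Stated type I error | 0.05 | 0.09 |
| Exact, p = 0.50 | 0.0396 | 0.0900 |
| Stated power | 80% | 80% |
| Exact, p = 0.70 | 0.8028 | 0.8009 |
| Probability of stopping at stage 1, p = 0.50 | 0.584 | 0.500 |
| Expected size, p = 0.50 | 29.5 | 21.5 |

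The 0.05 in 8.2.1 is a ceiling that the design respects. Lowering its rejection bound to 25 of 40 would give 0.0737. The ratio of the two exact error rates is 0.0900 / 0.0396 = 2.3.

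**Where the decisions part.**

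- *7 completions in the first 15.* Section 8.2.4 stops the study. Section 8.2.1 continues to 22 and needs 12 − 7 = 5 of the next 7 to pass stage 1: P(X ≥ 5 | 7, p) = 0.23 at p = 0.50 and 0.65 at p = 0.70.
- *18 completions in the first 28.* Section 8.2.4 rejects the null. Under 8.2.1 the first 22 hold at least 18 − 6 = 12 completions, so stage 1 is always passed, but 26 − 18 = 8 are still needed in 40 − 28 = 12 patients: P(X ≥ 8 | 12, p) = 0.19 at p = 0.50 and 0.72 at p = 0.70.

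**Can the two be read as one design?** The 28 patients at the MTD schedule plus up to 12 run-in patients at two abandoned schedules also make 40, so the 40 alone could be total enrolment. But 8.2.1 applies its rejection bound to 40 patients, and the abstract and 3.4 attach 0.05 to the design, not 0.09. That reading does not reconcile them.

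**Expansion size if 8.2.1 is kept.** With 6 run-in patients at the MTD schedule: 22 − 6 = 16 and 40 − 6 = 34.

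**The denominator.** If run-in patients at abandoned schedules count toward the 40, then 40 − 6 = 34 or 40 − 12 = 28 remain at the MTD schedule, and 26 of 40 cannot be applied. Keeping stage 1 at 22/11:

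| Final size and bound | Type I error, p = 0.50 | Power, p = 0.70 |
|---|---|---|
| ≥ 23 of 34 | 0.029 | 0.69 |
| ≥ 22 of 34 | 0.060 | 0.80 |
| ≥ 19 of 28 | 0.044 | 0.68 |

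A patient dosed for less than 14 days uses one of the 40 under 8.2.5 but leaves the analysis under 8.4.1. If two such patients left 38 analysed (an illustrative number) and the bound of 26 were kept, power would be 0.66.

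If instead the 40 counts only patients analysed at the MTD schedule and the run-in uses all 18, total enrolment can reach 40 + 12 = 52, before any patients dosed too briefly to be analysed.

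**The case against.** The strongest reply is that the intent is clear. The 40 appears in the abstract, 3.4, 8.2.1, 8.2.5 and 8.2.6, and the 0.05 in the abstract, 3.4 and 8.2.1, whereas only 8.2.3 and 8.2.4 carry the smaller design. Those two sections look like text left from an earlier design. This stands as an inference and as a reason for choosing the 40-patient design. It does not settle the matter: the section titled as the statistical plan holds the 28-patient rule, 8.2.3 sends the reader there, and nothing withdraws it.

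A reader might infer more than the documents support:

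- *That the 28-patient text contradicts itself,* because 8.2.4 places 28 in the expansion phase and 8.2.3 caps the expansion at 22. But 8.2.4 says its first 15 include 6 run-in patients, so 28 − 6 = 22 and the sizes agree. Only the phrase is loose.
- *That 8.3 adds a contradiction* by saying no interim analysis is planned. Both designs fully specify their futility look. Whether it is called an interim analysis is terminology and changes no decision.
- *That the 52% figure is part of the error.* Section 8.2.3 says the rate "will be determined and compared to a historical control rate of 52"%, but 8.2.1 openly states the 50% null beside the 52% rate. The choice of null arises under either design and is a separate question.
- *That the 0.05 in 8.2.1 is wrong.* An exact 0.040 satisfies a nominal 0.05.

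**Conclusion.** The point holds and must be fixed before stage-1 outcomes are known. Two full designs for the same test stand side by side. They have nearly equal power (0.803 and 0.801) but type I error of 0.040 and 0.090, and they give different decisions at results that could plausibly occur, such as 7 of 15 and 18 of 28. The calculations assume independent patients with a common completion rate and binding futility rules applied as written.

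The mismatch between 8.2.5 and 8.4.1 belongs to the same correction, because a bound of 26 of 40 works as stated only if 40 patients are actually analysed. How many would be lost is not known from the documents, so those figures are conditional illustrations.

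The documents do not show which design the sponsor intends. The preference for the 40-patient design rests mainly on the 0.05 repeated in the abstract and 3.4, since the 40 alone could be read as total enrolment.

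**What to change.** Before stage-1 outcomes are known, the sponsor confirms one design and states it identically in 8.2.1, 8.2.3 and 8.2.4. If the 22/11, 40/26 design is kept:

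1. Delete the 15/7, 28/18 rule from 8.2.4 and the 9, 22, 15 and 28 sizes from 8.2.3. The loose expansion-phase phrase goes with them.
2. Give the expansion as 16 to 34 patients, with 6 run-in patients at the MTD schedule counted in.
3. State the type I error as at most 0.05 (exact 0.040) at a null of 0.50.
4. Settle the denominator. Either state that 40 is the number analysed at the MTD schedule under 8.4.1, or give boundaries, type I error and power for the smaller number that will be analysed.

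Steps 1 to 3 are wording only and add no patients beyond the 40 already stated. Step 4 can cost more. If 40 means patients analysed at the MTD schedule, enrolment can reach 52 when the run-in uses all 18. The abstract, 3.4, 8.2.5 and 8.2.6 then need matching edits, and the 18-month accrual estimate in 8.2.6 should be checked. If 40 stays as the cap on all evaluable patients, the cost is lower power or a higher type I error, as the working shows.

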### **8.2.5 Replacement Policy**

A maximum of 40 evaluable patients will be enrolled in the study using a Simon's two-stage design for the primary endpoint. An evaluable patient will be defined as one who receives any amount of study drug. If a patient drops out of the study before receiving nivolumab, a replacement patient will be allowed.

### **8.2.6 Accrual estimates**

A maximum of 40 evaluable patients will be enrolled in the study using a Simon's two-stage design for the primary endpoint. At UCSF, approximately 20 NPC patients are treated with definitive radiation therapy yearly and we plan to partner with other high accruing centers. Thus we expect to be able to complete accrual to this study within a reasonable time frame.

It is anticipated that accrual will be completed in approximately 18 months, with each patient treated for approximately 6 months and then followed for 12 months after completing protocol therapy. The total study duration is expected to be about 3 years. If a longer duration of clinical follow-up is desired (such as 2 or 3 years), the timeline would lengthen by an additional year but that follow-up is at the discretion of the treating investigators and not mandated by the study.

## **8.3 Interim Analyses and Stopping Rules**

There is no interim analysis planned. There is a safety run-in which will be evaluated prior to continuing into the expansion phase. Safety of the study will be continuously assessed by the PI and the data safety monitoring committee (DSMC). The study may be stopped early if there is deemed to be an unacceptable safety risk by either the PI or the DSMC.

## **8.4 Analysis Plans**

### **8.4.1 Analysis Population**

Primary endpoint will be determined in patients who receive the study drug for a minimum of 1 cycle (or 14 days) at the MTD schedule.

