The very pressing question of whether there is any oncologic benefit to be accrued from the use of adjuvant chemotherapy in locoregionally advanced NPC was studied in a recent randomized trial from China. This phase III study compared RT with weekly CDDP followed either by 3 cycles of CDDP/5-FU or no adjuvant treatment. In 508 patients, the study found no statistically significant improvement in either progression-free or overall survival from the addition of adjuvant cytotoxic chemotherapy. Of note, in this study, 82% of patients assigned to the arm receiving weekly cisplatin plus adjuvant cisplatin-5FU started adjuvant chemotherapy, but only 63% were able to complete all 3 adjuvant cycles (52% therefore started and completed all adjuvant therapy). During adjuvant chemotherapy, 42% of patients experienced grade 3-4 toxic effects; 49% had dose reductions and 69% experienced delays in treatment. This is notable given that there was no apparent increase in rates of completion or better tolerance compared to results from the earlier era.

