### 3.4 Number of Subjects

A maximum of 40 evaluable patients will be enrolled in the study using a Simon's two-stage design for the primary endpoint. Patients who are enrolled at the maximally tolerated dose of

nivolumab during the run-in phase will be included in the determination of the primary endpoint. Non-evaluable patients will be replaced per the replacement policy (see section 8.2.5). For the primary endpoint, this design yields a type I error rate of 0.05 and power of 80% if the true rate of completion of adjuvant therapy is 0.7.

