a Each 14-day period of treatment will represent 1 cycle and begins from C1D1.b Baseline conditions assessmentc As part of efficacy assessments, quality of life by FACT-NP, FACT-Taxane, HHIE-S, and EuroQOL EQ-5D will be administered at baseline, at cycle 6, at end of treatment and at all followup visits. Survey's not available in the patient's language may be administered by the study staff in an interview format with a translator, however failure to obtain any individual quality of life survey not available in the patient's language will not be considered a protocol deviation.d Toxicity will be assessed by CTCAE v5.0f There is a 72 hour window of scheduled nivolumab administration. **In Dose Schedule 1:** Nivolumab will be administered on C1D1 for priming and then q14 days beginning C2D1, concurrent with chemoradiation, until C5D1. Nivolumab will not be administered on C6D1 to allow for any resolution of toxicities. Beginning C7D1, adjuvant nivolumab q14 days will be administered until C12D1. **In Dose Schedule 2:** Nivolumab will be administered on C1D1 concurrent with chemoradiation (no priming), and then q14 days until C4D1. Nivolumab will not be administered on C5D1 to allow for any resolution of toxicities. Beginning C6D1, adjuvant nivolumab q14 days will be administered until C11D1. **In Dose Schedule 3:** Nivolumab will not be administered until after completion of chemoradiation. Beginning C6D1, adjuvant nivolumab q14 days will be administered until C11D1. Immune-related toxicities should be at grade 1 or lower prior to starting a patient on the adjuvant phase of therapy; if not, initiation of the adjuvant phase should be delayed until resolution of toxicities.h Physical Exam includes weight measurementsi Disease-specific criteria (for CRF purposes, e.g.: GU assessment, BR disease Eval, AML-MDS Summary, etc.)j Measurable disease will be assessed using RECIST 1.1 criteriak For the **baseline** tissue collection, if a biopsy was performed within 90 days prior to C1D1, and no intervening treatment was given, a repeat biopsy is not required if adequate tumor tissue can be provided. **Repeat biopsy** will be at the discretion of the investigator, and timing will depend on Dose Schedule. **In Dose Schedule 1:** Tumor tissue post-nivolumab during cycle 1 AND after first week of radiation therapy. **In Dose Schedule 2 and 3:** Tumor tissue after first week of radiation therapy only. See appendix 4 for further details.l All blood draws may be completed within 7 days prior to start of therapy unless otherwise specified; screening labs must be completed within 14 days of Cycle 1 Day 1.m Hemoglobin, hematocrit, platelets, total white blood cell count (WBC) and differentialn Alkaline phosphatase, aspartate aminotransferase/alanine aminotransferase (ALT/AST), total bilirubin, total protein, albumin, calcium, phosphorus, magnesium, blood urea nitrogen (BUN), creatinine, glucose fasting), potassium, sodium, chloride, bicarbonate, uric acid, LDH, fasting lipid panel (LDL, total cholesterol, triglycerides), thyroid stimulating hormone (TSH).o **Pre-menopausal females:** serum or urine pregnancy test within 7 days prior to start of study drug. Serum pregnancy test by local laboratory  $\leq$  1 day prior to C1D1 for women of childbearing potential. If the serum pregnancy test results are not available on C1D1, a urine pregnancy test can be performed on C1D1 to confirm that the patient is not pregnant prior to dosing.p See Appendix 4 for details on tissue specimen collection and processing.q Collection of peripheral blood for correlative biomarkers and peripheral immune changes must be collected with every cycle of nivolumab. Blood will also be collected in post-treatment followup to 1 year.r Imaging with MRI nasopharynx/face/neck and whole body PET-CT will be performed at screening and at end of treatment and at 1 year followup, with further imaging to be performed as clinically indicated.

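### Under Dose Schedule 3 the completion rate leaves out patients who never start nivolumab, while its 52% benchmark counts non-starters as failures; sections 8.2.5 and 8.4.1 also disagree on who is evaluable

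*Combined protocol and SAP*

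**What the plan says.** Section 8.4.1 sets the primary analysis population: "Primary endpoint will be determined in patients who receive the study drug for a minimum of 1 cycle (or 14 days", treated at the MTD schedule. Section 8.2.5 sets evaluability differently: "An evaluable patient will be defined as one who receives any amount of study drug". It adds: "If a patient drops out of the study before receiving nivolumab, a replacement patient will be allowed".

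Two further passages say which run-in patients are pooled. Section 8.2.3 uses those treated: "The 6 patients treated at the final dose from the run-in cohort will be included in statistical comparisons". Section 3.4 refers to patients enrolled at the maximally tolerated dose and says that those given "nivolumab during the run-in phase will be included in the determination of the primary endpoint".

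The comparator comes from the randomized adjuvant chemotherapy trial described in section 1.1.2. On starting, that section reports that "82% of patients assigned to the arm receiving weekly cisplatin plus adjuvant cisplatin-5FU started adjuvant chemotherapy". On finishing, it gives the rate among those starters and then the product of the two rates: "only 63% were able to complete all 3 adjuvant cycles (52% therefore started and completed all adjuvant therapy"). Sections 8.1.1 and 8.2.3 compare this trial with that 52%, and sections 8.2.1 and 8.2.4 test it as a null of 50%, whichever schedule the run-in selects.

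For Dose Schedule 3, footnote f of Table 6.1 states: "Nivolumab will not be administered until after completion of chemoradiation". The first infusion is at C6D1, which is week 11.

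**The concern.** The endpoint is meant to show whether patients can get through the adjuvant phase. A patient who finishes or abandons chemoradiation and never begins adjuvant therapy is a failure on that endpoint, and the 52% treats such patients that way.

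At Schedules 1 and 2 nivolumab starts on C1D1, so these patients have already been dosed and stay in the denominator. At Schedule 3 they have had no nivolumab. They fall outside 8.4.1 and may be replaced under 8.2.5. The trial would then test a rate among starters against a benchmark for everyone assigned, and could be declared positive with no gain in completion.

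The conflict between 8.2.5 and 8.4.1 applies at every schedule. If a cycle or 14 days means more than one infusion, a patient dosed once and lost within two weeks is evaluable and cannot be replaced, yet is not analysed. The cut-offs assume exactly 40 or 28 analysed patients, and the plan does not say what happens if the number falls short. In an open-label single-arm trial, that leaves the primary denominator open to choice after the data are seen.

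**Working it through.** **Inputs.** Historical start rate 82% of assigned patients and completion rate 63% of starters (1.1.2). Benchmark 52% (8.1.1), null 0.50 and alternative 0.70 (8.2.1, 8.2.4). The plan contains two Simon designs, so both were used:
- Section 8.2.1: stop if 11 or fewer of 22; reject at 26 or more of 40.
- Section 8.2.4: stop if 7 or fewer of 15; reject at 18 or more of 28.

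**1. Reproduce the benchmark.** 0.82 × 0.63 = 0.517, or 52%. Its denominator is all assigned patients, including the 18% who never started. Among starters the rate is 63%.

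**2. Reproduce the designs.** With n1 and r1 the stage-1 size and stopping limit, n the total and r the rejection limit, the exact probability of success at true rate p is

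P(p) = Σ over x from r1+1 to n1 of Bin(x; n1, p) × Pr[Bin(n − n1, p) ≥ r − x].

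| True rate p | 26/40 rule | 18/28 rule |
|---|---|---|
| 0.50 | 0.040 (stated 0.05) | 0.090 (stated 0.09) |
| 0.70 | 0.803 (stated 0.80) | 0.801 (stated 0.80) |
| 0.52 | 0.066 | 0.129 |

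The last row shows what testing 0.50 instead of 0.52 does on its own. It is the baseline for what follows.

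**3. Schedule 3, true all-patient rate 52%.** If a share e never starts and is removed, the analysed rate is 0.52/(1 − e). The 18% is the historical cisplatin-5FU figure; 5%, 10% and 25% are assumptions.

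| e | Analysed rate | 26/40 | Excess over e = 0 | 18/28 | Excess over e = 0 |
|---|---|---|---|---|---|
| 0 | 0.520 | 0.066 | – | 0.129 | – |
| 5% | 0.547 | 0.124 | 0.057 | 0.201 | 0.071 |
| 10% | 0.578 | 0.220 | 0.154 | 0.303 | 0.174 |
| 18% | 0.634 | 0.483 | 0.417 | 0.538 | 0.409 |
| 25% | 0.693 | 0.776 | 0.709 | 0.778 | 0.649 |

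The historical behaviour itself (82% start, 63% of those complete) gives 0.061 under 26/40 and 0.122 under 18/28 with everyone counted, and 0.46 and 0.52 with starters only. At an 82% start rate, 40 starters need about 40/0.82 ≈ 49 enrolled, so 26 completions is 26/49 = 53% of those enrolled, about the historical rate.

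**4. Chance of reaching Schedule 3.** This needs 3 or more DLTs in 6 patients at Schedule 1 and again at Schedule 2. With equal, independent DLT rates, the chance is Pr[Bin(6, d) ≥ 3]². For assumed d of 20%, 33% and 40% it is 0.010, 0.102 and 0.208.

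**5. Schedules 1 and 2.** Only patients dosed but lost within 14 days are affected, and only if the minimum means more than one dose. With 1%, 2% or 5% lost (assumptions), success at a true 52% has probability 0.075, 0.086 or 0.124 under 26/40 and 0.142, 0.155 or 0.201 under 18/28. Section 2.4.1 may partly offset this, because it also requires concurrent nivolumab to be completed.

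**The case against.** The strongest objection is that Schedule 3 is unlikely. The one related toxicity figure in the documents is the 13.1% grade 3/4 rate with nivolumab in the head and neck trial described in section 1.2.3.1. At that rate, Pr[Bin(6, 0.131) ≥ 3] = 0.033 and its square is about 0.1%. But that figure is for nivolumab without chemoradiation in another population, and the DLT definition here also covers long holds and interrupted chemoradiation. It stands as a reason to treat this branch as a contingency. It does not excuse a rule that fails there, since Schedule 3 is prespecified and can become the MTD schedule.

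Second, the term study drug in 8.4.1 might cover more than nivolumab. Table 5.1 lists radiation and cisplatin under that heading, section 5.2.2 uses the term in the cisplatin interruption rule, and Schedule 3 cycles are counted from the start of chemoradiation. On that reading, non-starters could stay in. However, the abstract lists only nivolumab as a study drug, and the replacement sentence in 8.2.5 names nivolumab. The wider reading also makes 8.2.5 contradict itself: a patient given only chemoradiation would be both evaluable and replaceable. Either reading needs repair.

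Third, the non-starter shares are not evidence about this regimen, and 25% exceeds even the historical figure. That is fair; the table shows sensitivity and is not a forecast.

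Fourth, sections 3.4 and 8.2.3 mainly identify which run-in cohort is pooled. This is largely right. The direct contradiction is between 8.2.5 and 8.4.1, and the difference between enrolled and treated only adds looseness.

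**Conclusion.** The concern holds and should be fixed. Taking study drug to mean nivolumab, the plan under Schedule 3 compares a starters-only rate with an all-assigned benchmark. The historical gap between the two is 63% against 52%. With a true all-patient rate of 52%, the exclusion alone adds 0.06 to 0.15 to the chance of a false success under 26/40 if 5% to 10% never start, and 0.42 at the historical 18%. Under 18/28 the additions are 0.07 to 0.17, and 0.41.

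This is conditional on a branch whose chance is about 1% to 21% at the assumed DLT rates, and lower at the one related figure in the documents. On the planned path the bias is small. The evaluability conflict does not depend on the schedule and needs settling in any case.

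**What to change.** In 8.4.1 and 8.2.5, define the primary population as all patients enrolled at the MTD schedule who begin any protocol treatment, whether nivolumab or chemoradiation. Count anyone who never starts, or does not finish, adjuvant nivolumab as a non-completer. Allow replacement only before any protocol treatment. Use the same definition in 3.4 and 8.2.3, and name the treatment wherever 8.4.1 and 8.2.5 now say study drug. Report completion among adjuvant starters as a secondary result, against 63%. Patients enrolled but never treated would still be replaced, so the match to an assigned denominator is close but not perfect.

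Raising the null to 63% and keeping a starters-only population would be worse. With the same first stage, 31 or more of 40 would be needed (exact type I error 0.038), and power at 0.70 would be 0.20.

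The cost is a few paragraphs of wording, with no added patients or procedures. The observed completion rate will be lower: slightly at Schedules 1 and 2, and possibly by about 10 points at Schedule 3, going by 63% against 52% in the historical trial. Power stays at 0.80 if the assumed 70% describes the whole regimen, as 8.2.1 words it. If 70% is really a starters' rate, the Schedule 3 rate is 0.70 × (1 − e): 0.665, 0.630 or 0.574 for 5%, 10% or 18% non-starters. Power under 26/40 is then 0.64, 0.46 or 0.21. The sponsor should state which is meant.
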